# **SYNOPSIS**

Title of Study:	A Randomized, Single-Dose, Open-Label, Parallel-Group Study in Healthy Volunteers to Assess the Relative Bioavailability of a Subcutaneous Dose of Nemolizumab When Administered with Auto-Injector Compared to Dual-Chamber Syringe
Protocol Number:	RD.06.SPR.201590
Investigators/Stud y Sites:	Approximately 3 study sites are planned in the United States
Phase of Development:	Phase 1
Objectives:	The primary objective is to compare the rate and extent of absorption a single dose of nemolizumab administered with auto-injectors (AI; test) versus dual-chamber syringes (DCS; reference) under controlled conditions in healthy adult subjects.
	The secondary objectives are to assess the safety and immunogenicity of nemolizumab following administration with AI or DCS in healthy adult subjects.
Study Endpoints:	Primary Endpoints:
	Change of primary pharmacokinetic (PK) parameters: C max (rate of absorption) and AUC 0-inf (extent of absorption) of nemolizumab administered with AI or DCS
	Secondary Endpoints:
	Change of secondary PK parameters (AUC 0-4 weeks AUC 0-last , T max , and t 1/2 ) of nemolizumab administered with AI or DCS
	Assessment of the immunogenicity (anti-drug antibodies, ADA) of nemolizumab administered with AI or DCS
	• CCI
Study Design:	This is a randomized, multicenter, open-label, single-dose, parallel-group study in healthy adult subjects aged 18 to 65 years to assess the relative bioavailability of a 60-mg subcutaneous dose of nemolizumab administered with AI compared to DCS, stratified by injection site. The 60-mg dose will be administered as 2 successive subcutaneous injections of 30 mg (AI or DCS).
	The study duration will be up to 16 weeks and consists of an up to 28-day screening period and a 12-week PK evaluation period.
	The screening period will evaluate subject eligibility. At baseline, approximately 192 subjects will be randomized 1:1 to receive 60 mg nemolizumab delivered with either AI or DCS. Subjects will be further randomized 1:1:1 to receive injection in 1 of 3 injection sites, i.e., abdomen, front upper thigh, or outer upper arm. Approximately 32 subjects in each delivery group will be assigned to each injection site.
	Subjects will receive a 60-mg dose of nemolizumab via 2 subcutaneous injections of 30 mg nemolizumab. Injections should be administered at the same location (i.e., abdomen, front upper thigh, or outer upper arm) on the same side with injection sites at least 1 inch (2.5 cm) apart. Blood samples will be collected before and after nemolizumab administration for up to 12 weeks post-dose for determining the complete serum PK profile of nemolizumab.

A total of 21 blood samples will be collected, i.e., 1 before and 20 after nemolizumab administration (i.e., pre-dose, 12 hours, 24 hours, 3, 4, 5, 6, 7, 8, 9, 10, 11, 15, 22, 29, 36, 43, 50, 57, 71, and 85 days post-dose). Subjects will be confined to the study center for 1 night, from nemolizumab dosing (Day 0) to the morning after nemolizumab dosing (Day 1).

Clinical assessments will occur according to the Schedule of Assessments. **Figure 1** presents an overview of the study design.

Figure 1 Study Design

R: randomization

D0: injection day, the pre-dose PK sample will be collected before nemolizumab administration.

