### 7.2 Study Rationale

During the course of development, nemolizumab in an auto-injector (AI) has been introduced. The AI is a fully disposable, single-use and single-dose injection system intended for subcutaneous injections (see Section 11.1). The AI facilitates subcutaneous injections by patients or caregivers and is the intended presentation for commercial use.

The AI is assembled around a dual-chamber cartridge, containing the same nemolizumab formulation as the DCS. To use information gathered from the DCS development program for support of a marketing authorization application with an AI, a gap analysis was performed in accordance with the Food and Drug Administration (FDA) draft guidance "Bridging for Drug-Device and Biologic-Device-Combination Products". Further chemistry, manufacturing and control data will be generated based on the information identified in the gap analysis. In addition, the current PK study will address the impact of changes in in the drug delivery parameters between AI and DCS (i.e. injection depth, injection angle and injection time)

The bridging strategy includes this PK study to assess the relative bioavailability of a subcutaneous dose of nemolizumab when administered with an AI in comparison to a DCS. The primary objective of this study is to compare the rate ( $C_{max}$ ) and extent (AUC) of absorption of a single 60-mg dose of nemolizumab administered with AI (test) versus DCS (reference) under controlled conditions in healthy adult subjects. The secondary objectives are to assess the safety and immunogenicity of nemolizumab following administration with AI or DCS in healthy adult subjects.

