### 8.2 Study Endpoints

### 8.2.1 Primary Endpoint

Change of primary pharmacokinetic (PK) parameters: Cmax (rate of absorption) and AUC0-inf (extent of absorption) of nemolizumab administered with AI or DCS

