# 9.2 Discussion of Study Design

This study will assess the relative bioavailability of a 60-mg subcutaneous dose of nemolizumab administered with AI compared to DCS, stratified by injection site, including abdomen, front upper thigh, or outer upper arm. Overall, a single-dose, open-label, parallel-group PK study in healthy adult subjects is deemed appropriate for this purpose.

The parallel-group design of this study is considered necessary due to the long terminal half-life of nemolizumab ranging from 12.6 to 16.5 days and is in line with the FDA guidance "Clinical Pharmacology Data to Support a Demonstration of Biosimilarity to a Reference Product" (Guideline 2016) and the corresponding European guideline (Guideline 2014).

In accordance with the same FDA guidance, the study plans a single-dose administration, since single-dose PK studies are generally more sensitive than steady-state studies in assessing any difference in rate and extent of release of the drug substance from the drug product into the systemic circulation. Furthermore, in the case of nemolizumab, repeated-dose studies demonstrated a limited systemic accumulation over time, with median accumulation below 2, and steady-state concentrations reached after the loading dose. This confirms that the PK profile of nemolizumab is not affected by the number of administrations and can be predicted from single-dose PK parameters.

The choice of heathy adult subjects is supported by the results of the Phase 1 study CIM001JP. Study CIM001JP showed that nemolizumab concentration-time profiles in AD patients and healthy subjects shared the same shape, being described in both groups by a one-compartment distribution model with linear elimination and first-order absorption. Overall, nemolizumab systemic exposure

increased in a dose-dependent manner in the dose range of 0.03 to 3 mg/kg. The only observed difference was a 23 to 26% reduced exposure in AD patients compared with healthy subjects. Owing to its low immunogenicity potential, there are no safety concerns associated with nemolizumab that will preclude investigation in healthy subjects. In addition, the type of disease does not have any effect on nemolizumab PK, as similar systemic exposure and similar PK profiles were observed in subjects with AD (Phase 2 study CIM003JG) and in subjects with PN (Phase 2 study SPR.115828) when treated with the same dose of 0.5 mg/kg.

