# 17.1 Determination of Sample Size

From previous studies conducted with nemolizumab, inter-subject standard deviation is expected to be approximately 38.5%, which provides an inter-subject variability CV for the primary PK parameters of 40%. A sample size of 96 subjects per arm (AI or DCS) should provide a 90% power of claiming the bioequivalence between AI and DCS administration within the range 80.00 to 125.00% for the primary PK parameters with the expected GMR of 0.95.

Approximately 192 healthy subjects are planned to be randomized in this study.

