# 17.3 Statistical Analysis of Pharmacokinetic Parameters

# 17.3.1 Primary Pharmacokinetic Endpoints

For the primary PK endpoint analyses, a linear mixed-effect model will assess the log transformed PK parameters (AUC $_{0\text{-inf}}$  and  $C_{max}$ ) of nemolizumab, with treatment (administration with AI or DCS) and injection site as fixed effects and subject as a random effect. Some clinically important baseline characteristics may also be included in the model. The AUC and  $C_{max}$  GMR between treatments (nemolizumab administered with AI [test] or DCS [reference]) after backtransformation and the corresponding 90% CI will be provided overall.

Acceptance criterion for bioequivalence is a 90% CI for the test/reference ratio of the geometric means of the parameters under consideration within the 80.00 to 125.00% range.

In addition, the GMR and 90% CI will be provided by injection site for information only.

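### Cmax carries the rate half of the primary objective, but on the protocol's own pharmacokinetics it responds only weakly to absorption rate, so a pass should be read as equivalence in peak and total exposure

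*Protocol*

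**What the plan says.** The synopsis and Section 8.1.1 give a primary objective in two halves: "The primary objective is to compare the rate and extent of absorption a single dose of nemolizumab administered with auto-injectors" (AI) against the dual-chamber syringe (DCS). Section 8.2.1 ties each half to one parameter, in the words "rate of absorption) and AUC": Cmax stands for rate and AUC0-inf for extent. Section 7.2 says why rate is of interest: "the current PK study will address the impact of changes in in the drug delivery parameters between AI and DCS", naming injection depth, angle and time.

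Section 17.3.1 sets the decision rule: "Acceptance criterion for bioequivalence is a 90% CI for the test/reference ratio of the geometric means" inside 80.00 to 125.00%. Section 17.3.2 analyses AUC0-last, AUC0-4 weeks and half-life in the same way as the primary parameters. Tmax gets only a Wilcoxon signed-rank test.

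Section 9.2 describes the pharmacokinetics. It cites the "long terminal half-life of nemolizumab ranging from 12.6 to 16.5 days", an expected Tmax of 5 to 9 days, and concentration profiles "being described in both groups by a one-compartment distribution model with linear elimination and first-order absorption". Samples at 12 hours, 24 hours and Day 3 are scheduled for every subject, but no parameter in Section 16 isolates that period.

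**The concern.** When absorption is several times faster than elimination, the peak depends mainly on how much drug is absorbed and only slightly on how quickly. Cmax then behaves largely as a second measure of extent. If it is read under its protocol label, a trial that meets the criterion could be reported as showing equivalent rates of absorption when one device delivers drug to the circulation appreciably faster or slower than the other.

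No other planned parameter supplies an interval on a rate-sensitive quantity. AUC0-4 weeks is less sensitive to rate than Cmax. A Tmax test that is not significant does not show that rates are similar. At stake is the wording of half of the primary conclusion, not the bioequivalence decision.

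**Working it through.** **Inputs.** All are from the protocol except the change in absorption rate: half-life 12.6 to 16.5 days, Tmax 5 to 9 days and the one-compartment first-order model (Section 9.2); 96 per arm and "inter-subject standard deviation is expected to be approximately 38.5"% (Section 17.1); acceptance range 80.00 to 125.00% (Section 17.3.1). The factors 1.5, 2 and 2/3 are illustrations. Bioavailability, volume and elimination are held fixed.

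**The plan's own figure.** A log-scale SD of 0.385 gives a CV of √(exp(0.385²) − 1) = 0.40, as stated. Two one-sided tests with 96 per arm and a true ratio of 0.95 have 92.4% power. With 0.40 used directly as the log SD, power is 90.6%. The stated 90% is sound.

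**Absorption rate implied by the protocol.** With ke = ln 2 / half-life, solve ln(ka/ke)/(ka − ke) = Tmax for ka. Over the stated ranges ka is 3.6 to 13 times ke.

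**Effect on Cmax.** In this model the ratio of peaks is exp(−ke × (new Tmax − old Tmax)). For 1.5 times faster absorption:
- Half-life 12.6 d, Tmax 9 d: ke = 0.0550 and ka = 0.196, raised to 0.294. Tmax falls to 7.00 d, and the ratio is exp(0.0550 × 2.00) = 1.116.
- Half-life 16.5 d, Tmax 5 d: ke = 0.0420 and ka = 0.560, raised to 0.840. Tmax falls to 3.75 d, and the ratio is exp(0.0420 × 1.25) = 1.054.

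**Probability of acceptance.** The standard error is 0.385 × √(2/96) = 0.0556. The half-width of the 90% CI is 1.653 × 0.0556 = 0.0919, so the observed ratio must fall below 1.25/exp(0.0919) = 1.140. At a true ratio of 1.116, (ln 1.140 − ln 1.116)/0.0556 ≈ 0.39, which gives 65%. At 1.054 it is about 1.42, which gives 92%.

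**All cases**, using the maximum over the scheduled samples, and for the early area the linear trapezoid over 0, 0.5, 1 and 3 days:

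| Absorption rate | Cmax ratio | Cmax accepted | AUC0-3 days ratio |
|---|---|---|---|
| ×1.5 | 1.05–1.12 | 65–92% | 1.22–1.36 |
| ×2 | 1.09–1.19 | 22–81% | 1.37–1.66 |
| ×2/3 | 0.875–0.93 | 48–87% | 0.71–0.78 |

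AUC0-4 weeks moves by only 1 to 5% at ×1.5. A true Cmax ratio of 1.25 would need absorption 2.6 to 9.7 times faster. At half-life 16.5 d and Tmax 5 d it is never reached, because the ceiling is exp(0.0420 × 5) = 1.23.

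**Sensitivity of the ×1.5 result.** With log SD 0.40, or with 88 evaluable per arm, Cmax acceptance is 62 to 90%. Requiring AUC0-inf to pass as well (true ratio 1, assumed correlation 0.5 to 0.8) gives about 64 to 91%.

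**Behaviour of the early area under identical devices.** Its variability is not given. At SD 0.385 identical devices would meet 80.00 to 125.00% about 98% of the time. At an assumed SD of 0.60 they would do so only about 64% of the time.

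**The case against.** The strongest reply is that nothing here is contradictory. The protocol defines rate through Cmax throughout, sets one criterion for it, and names no rate difference that it must detect. A true Cmax ratio of 1.05 to 1.12 lies inside the range, so accepting it is correct. A reader might take 65 to 92% as a false-acceptance rate, or conclude that the criterion or the sample size is wrong. The documents do not support either reading.

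Nor can one say that the trial is blind to rate. At twice the rate Cmax fails 19 to 78% of the time.

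Tmax also has real value. It is sampled daily from Day 3 to Day 11, and at ×1.5 it shifts by about 22 to 25%. A two-sample rank test with 96 per arm would have roughly 99% power at an assumed Tmax CV of 40%, and 68 to 74% at 80%. The test named in Section 17.3.2, however, is for paired data and the arms are independent. Even once corrected, it gives no interval.

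Two further replies hold in part. The early concentrations will be listed, summarised and plotted by device (Section 16), so they are not hidden. The SAP or PK plan might add parameters, but the Cmax label and the endpoint list are fixed in the protocol. It is also conjecture, not protocol content, that depth, angle and time act mainly on early absorption.

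What stands: a pass on Cmax is weak evidence about rate, and no planned interval supplements it.

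**Conclusion.** The concern holds as a limit on interpretation. On the protocol's own half-life, Tmax and model, a 1.5-fold faster absorption moves Cmax by 5 to 12% and passes about 65 to 92% of the time; one third slower passes 48 to 87%. These figures assume unchanged bioavailability, a log SD of 0.385 and 96 evaluable per arm, and the size of the rate change is illustrative.

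The bioequivalence criterion, the primary endpoints and the sample size are sound and need no change. What the design does not support is the step from a Cmax pass to a statement that rates of absorption are equivalent. Data that bear on rate more directly are already scheduled, which makes this a cheap improvement worth making.

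**What to change.** Keep Cmax, AUC0-inf, the sample size and the acceptance criterion as they are.

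- Add the AUC from dosing to the Day 3 sample (pre-dose, 12-hour, 24-hour and Day 3 samples) to the secondary PK parameters in the synopsis and Sections 8.2.2, 16 and 17.3.2.
- Report its AI/DCS geometric mean ratio and 90% CI from the primary model, descriptively. Do not apply 80.00 to 125.00% to it, because its variability is not given and may exceed that of Cmax.
- Replace the signed-rank test for Tmax with a two-sample comparison.
- Describe a pass on the primary endpoints as equivalence in peak and total exposure. Base any statement on rate of absorption on Cmax together with the early area and Tmax.

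The cost is a wording change and one more line in the secondary PK table, with no new samples or subjects. The downside is that an early difference between devices, once it has an interval, may need explaining.

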# Selection of **Subjects**:

### Inclusion Criteria

Individuals must meet all of the following criteria to be included in the study:

- 1. Male and female subjects aged 18 to 65 years at the screening visit.
- 2. Body weight  $\geq$  45 kg and body mass index between  $\geq$  18.0 and  $\leq$  30.0 kg/m^2 at both screening and baseline visits.
- 3. Medically healthy with normal clinical status as judged by the investigator based on medical history, physical examination, and clinical laboratory tests.
- 4. Willing to abstain from all prescription medications during the study, (defined hereafter as after signing of informed consent form), except to treat AEs and contraception and as permitted under Exclusion 2. Limited use of non-prescription medications/supplements that are not believed to affect subject's safety or the overall results of the study may be permitted at the discretion of the investigator.
- 5. Female subjects of childbearing potential (i.e., fertile, after menarche and, until becoming postmenopausal unless permanently sterile) must agree either to be strictly abstinent throughout the study and for 12 weeks after the study drug injection, or to use an adequate and approved method of contraception throughout the study and for 12 weeks after the study drug injection. Males are not required to use contraception, and there is no restriction on sperm donation.

Adequate and approved methods of contraception applicable for the subject and/or her partner are:

- Progestogen-only oral hormonal contraception.
- Combination of male condom with cervical cap, vaginal diaphragm, or vaginal sponge with spermicide (double barrier methods).

- Note: "Double barrier methods" refer to simultaneous use of a physical barrier by each partner. Use of a single barrier method (e.g., condom) with a spermicide is not acceptable.
  - Combined (estrogen- and progestogen-containing) oral, intravaginal, or transdermal hormonal contraception.
  - Injectable or implanted hormonal contraception.
  - Intrauterine devices or intrauterine hormone-releasing system.
  - Bilateral tubal ligation or tube insert (such as the Essure system) at least 3 months before the study.
  - Bilateral vasectomy of partner at least 3 months before the study.
- 6. Female subjects of non-childbearing potential must meet one of these criteria:
  - Absence of menstrual bleeding for 1 year before the screening visit with no other medical reason, confirmed with follicle-stimulating hormone (FSH) level in the postmenopausal range.
  - Documented hysterectomy, bilateral salpingectomy, or bilateral oophorectomy at least 3 months before the study.
  - Note: Bilateral tubal ligation is not accepted as reason for non-childbearing potential.
- 7. Willing and able to comply with all of the time commitments and procedural requirements of the clinical study protocol.
- 8. Understand and sign an informed consent form before any investigational procedure(s) are performed.

[figure not shown]
### **Exclusion Criteria**

[figure not shown]
Individuals meeting any of the following criteria at the screening or baseline visit are ineligible to participate in this study:

- 1. History of hypersensitivity (including anaphylaxis) to an immunoglobulin product (plasma-derived or recombinant, e.g., monoclonal antibody) or to any of the study drug excipients.
- 2. Cutaneous infection within 1 week before the baseline visit or any infection requiring treatment with oral, parenteral antibiotics, antivirals, antiparasitics, or antifungals within 2 weeks before the baseline visit. Note: Subjects with chronic, stable use of prophylactic treatment for recurrent herpes viral infection can be included in this clinical study.
- 3. Any confirmed or suspected coronavirus disease (COVID-19) infection within 2 weeks before the screening or baseline visit. Subjects may be rescreened once the infection has resolved. Resolution of COVID-19 infection can be confirmed by recovery assessment methods, as described in the protocol.
- 4. Positive serology results (hepatitis B surface antigen [HBsAg] or hepatitis B core antibody [HBcAb], hepatitis C [HCV] antibody with positive HCV RNA, or human immunodeficiency virus [HIV] antibody) at the screening visit.

Note: Subjects with a positive HBcAb and a negative HBsAg can be included if the hepatitis B surface antibody is positive (considered immune after a natural infection). Subjects who are positive for HCV antibody and negative for HCV RNA can be included.

In the event of rescreening, the serology tests results (e.g., HBV, HCV, HIV) from the first screening can be used by the investigator to assess the eligibility of rescreened subjects if those tests were performed within 6 weeks before the baseline visit.  5. Known active or untreated latent tuberculosis (TB) infection.  Note: Subjects who have a documented history of completion of an appropriate TB treatment regimen for active or latent TB with no history of re-exposure to TB since their treatment was completed are eligible to participate in the study.  6. Known or suspected immunosuppression or unusually frequent, recurrent, severe, or prolonged infections as per investigator judgment.  7. History of lymphoproliferative disease or history of malignancy of any organ system within the last 5 years, except for (1) basal cell carcinoma, squamous cell carcinoma in situ (Bowen's disease), or carcinoma in situ of the cervix that have been treated and have no evidence of recurrence in the last 12 weeks before the baseline visit, or (2) actinic keratoses that have been treated.  8. Any condition that may interfere with study assessments (e.g., poor venous access or needle phobia).  9. Having received a live-attenuated or non-live vaccine within 4 weeks before the baseline visit or are expected to be vaccinated during the study or during the 12 weeks after the study drug injection, except for non-live seasonal vaccinations (e.g., influenza), COVID-19 and/or emergency vaccinations (e.g., rabies, tetanus), which are permitted during the study.  10. Previous treatment with nemolizumab.  11. History of alcohol or substance abuse within 6 months of the screening visit.  12. Planned or expected major surgical procedure during the clinical study.  13. Pregnant women (positive serum pregnancy test result at the screening visit or positive urine pregnancy during the study or 12 weeks after the study drug injection.  14. Subjects who have donated ≥ 500 mL of blood in the 3 months before dosing.  15. Participating or participate		,
Note: Subjects who have a documented history of completion of an appropriate TB treatment regimen for active or latent TB with no history of re-exposure to TB since their treatment was completed are eligible to participate in the study.  6. Known or suspected immunosuppression or unusually frequent, recurrent, severe, or prolonged infections as per investigator judgment.  7. History of lymphoproliferative disease or history of malignancy of any organ system within the last 5 years, except for (1) basal cell carcinoma, squamous cell carcinoma in situ (Bowen's disease), or carcinomas in situ of the cervix that have been treated and have no evidence of recurrence in the last 12 weeks before the baseline visit, or (2) actinic keratoses that have been treated.  8. Any condition that may interfere with study assessments (e.g., poor venous access or needle phobia).  9. Having received a live-attenuated or non-live vaccine within 4 weeks before the baseline visit or are expected to be vaccinated during the study or during the 12 weeks after the study drug injection, except for non-live seasonal vaccinations (e.g., influenza), COVID-19 and/or emergency vaccinations (e.g., rabies, tetanus), which are permitted during the study.  10. Previous treatment with nemolizumab.  11. History of alcohol or substance abuse within 6 months of the screening visit.  12. Planned or expected major surgical procedure during the clinical study.  13. Pregnant women (positive serum pregnancy test result at the screening visit or positive urine pregnancy test at the baseline visit), breastifeeding women, or women planning a pregnancy during the study or 12 weeks after the study drug injection.  14. Subjects who have donated ≥ 500 mL of blood in the 3 months before dosing.  15. Participating or participated in any other study with an investigational drug or device within the past 8 weeks (of 5 half-lives of the investigational drug, whichever is longer) before the screening visit, or is in an exclusion period (if verifiable) from a previous s		
treatment regimen for active or latent TB with no history of re-exposure to TB since their treatment was completed are eligible to participate in the study.  6. Known or suspected immunosuppression or unusually frequent, recurrent, severe, or prolonged infections as per investigator judgment.  7. History of lymphoproliferative disease or history of malignancy of any organ system within the last 5 years, except for (1) basal cell carcinoma, squamous cell carcinoma in situ (Bowen's disease), or carcinomas in situ of the cervix that have been treated and have no evidence of recurrence in the last 12 weeks before the baseline visit, or (2) actinic keratoses that have been treated.  8. Any condition that may interfere with study assessments (e.g., poor venous access or needle phobia).  9. Having received a live-attenuated or non-live vaccine within 4 weeks before the baseline visit or are expected to be vaccinated during the study or during the 12 weeks after the study drug injection, except for non-live seasonal vaccinations (e.g., influenza), COVID-19 and/or emergency vaccinations (e.g., rabies, tetanus), which are permitted during the study.  10. Previous treatment with nemolizumab.  11. History of alcohol or substance abuse within 6 months of the screening visit.  12. Planned or expected major surgical procedure during the clinical study.  13. Pregnant women (positive serum pregnancy test result at the screening visit or positive urine pregnancy test at the baseline visit), breastfeeding women, or women planning a pregnancy during the study or 12 weeks after the study drug injection.  14. Subjects who have donated ≥ 500 mL of blood in the 3 months before dosing.  15. Participating or participated in any other study with an investigational drug or device within the past 8 weeks (or 5 half-lives of the investigational drug, whichever is longer) before the screening visit, or is in an exclusion period (if verifiable) from a previous study.  Planned Sample  From previous studies conducted with nemolizumab, inter-su		5. Known active or untreated latent tuberculosis (TB) infection.
Prolonged infections as per investigator judgment.  7. History of lymphoproliferative disease or history of malignancy of any organ system within the last 5 years, except for (1) basal cell carcinoma, squamous cell carcinoma in situ (Bowen's disease), or carcinomas in situ of the cervix that have been treated and have no evidence of recurrence in the last 12 weeks before the baseline visit, or (2) actinic keratoses that have been treated.  8. Any condition that may interfere with study assessments (e.g., poor venous access or needle phobia).  9. Having received a live-attenuated or non-live vaccine within 4 weeks before the baseline visit or are expected to be vaccinated during the study or during the 12 weeks after the study drug injection, except for non-live seasonal vaccinations (e.g., influenza), COVID-19 and/or emergency vaccinations (e.g., rabies, tetanus), which are permitted during the study.  10. Previous treatment with nemolizumab.  11. History of alcohol or substance abuse within 6 months of the screening visit.  12. Planned or expected major surgical procedure during the clinical study.  13. Pregnant women (positive serum pregnancy test result at the screening visit or positive urine pregnancy test at the baseline visit), breastfeeding women, or women planning a pregnancy during the study or 12 weeks after the study drug injection.  14. Subjects who have donated ≥ 500 mL of blood in the 3 months before dosing.  15. Participating or participated in any other study with an investigational drug or device within the past 8 weeks (or 5 half-lives of the investigational drug, whichever is longer) before the screening visit, or is in an exclusion period (if verifiable) from a previous study.  Planned Sample  Size:  From previous studies conducted with nemolizumab, inter-subject standard deviation is expected to be approximately 38.5%, which provides an inter-subject standard deviation of variation (CV) for the primary PK parameters of 40%. A sample size of 96 subjects per arm (AI or DCS) should provide a		treatment regimen for active or latent TB with no history of re-exposure to TB since
within the last 5 years, except for (1) basal cell carcinoma, squamous cell carcinoma in situ (Bowen's disease), or carcinomas in situ of the cervix that have been treated and have no evidence of recurrence in the last 12 weeks before the baseline visit, or (2) actinic keratoses that have been treated.  8. Any condition that may interfere with study assessments (e.g., poor venous access or needle phobia).  9. Having received a live-attenuated or non-live vaccine within 4 weeks before the baseline visit or are expected to be vaccinated during the study or during the 12 weeks after the study drug injection, except for non-live seasonal vaccinations (e.g., influenza), COVID-19 and/or emergency vaccinations (e.g., rabies, tetanus), which are permitted during the study.  10. Previous treatment with nemolizumab.  11. History of alcohol or substance abuse within 6 months of the screening visit.  12. Planned or expected major surgical procedure during the clinical study.  13. Pregnant women (positive serum pregnancy test result at the screening visit or positive urine pregnancy test at the baseline visit), breastfeeding women, or women planning a pregnancy during the study or 12 weeks after the study drug injection.  14. Subjects who have donated ≥ 500 mL of blood in the 3 months before dosing.  15. Participating or participated in any other study with an investigational drug or device within the past 8 weeks (or 5 half-lives of the investigational drug, whichever is longer) before the screening visit, or is in an exclusion period (if verifiable) from a previous study.  Planned Sample  Size:  From previous studies conducted with nemolizumab, inter-subject standard deviation is expected to be approximately 38,5%, which provides an inter-subject variability coefficient of variation (CV) for the primary PK parameters of 40%. A sample size of 96 subjects per arm (AI or DCS) should provide a 90% power of claiming the bioequivalence between AI and DCS administrations within the range 80.00 kA. a sample size of 96 subjects p		
9. Having received a live-attenuated or non-live vaccine within 4 weeks before the baseline visit or are expected to be vaccinated during the study or during the 12 weeks after the study drug injection, except for non-live seasonal vaccinations (e.g., influenza), COVID-19 and/or emergency vaccinations (e.g., rabies, tetanus), which are permitted during the study.  10. Previous treatment with nemolizumab.  11. History of alcohol or substance abuse within 6 months of the screening visit.  12. Planned or expected major surgical procedure during the clinical study.  13. Pregnant women (positive serum pregnancy test result at the screening visit or positive urine pregnancy test at the baseline visit), breastfeeding women, or women planning a pregnancy during the study or 12 weeks after the study drug injection.  14. Subjects who have donated ≥ 500 mL of blood in the 3 months before dosing.  15. Participating or participated in any other study with an investigational drug or device within the past 8 weeks (or 5 half-lives of the investigational drug, whichever is longer) before the screening visit, or is in an exclusion period (if verifiable) from a previous study.  Planned Sample  Size:  Prom previous studies conducted with nemolizumab, inter-subject standard deviation is expected to be approximately 38.5%, which provides an inter-subject variability coefficient of variation (CV) for the primary PK parameters of 40%. A sample size of 96 subjects per arm (AI or DCS) should provide a 90% power of claiming the bioequivalence between AI and DCS administrations within the range 80.00 to 125.00% for the primary PK parameters with the expected geometric mean ratio of 0.95.  Approximately 192 healthy subjects are planned to be randomized in this study.  Nemolizumab (CD14152) 30 mg will be provided for injection for subcutaneous use only after reconstitution in a single-use, prefilled DCS or in a single-use, prefilled ACS subjects will receive a 60-mg dose of nemolizumab via 2 subcutaneous injections of 30 mg each at the ba		within the last 5 years, except for (1) basal cell carcinoma, squamous cell carcinoma in situ (Bowen's disease), or carcinomas in situ of the cervix that have been treated and have no evidence of recurrence in the last 12 weeks before the baseline visit, or
visit or are expected to be vaccinated during the study or during the 12 weeks after the study drug injection, except for non-live seasonal vaccinations (e.g., influenza), COVID-19 and/or emergency vaccinations (e.g., rabies, tetanus), which are permitted during the study.  10. Previous treatment with nemolizumab.  11. History of alcohol or substance abuse within 6 months of the screening visit.  12. Planned or expected major surgical procedure during the clinical study.  13. Pregnant women (positive serum pregnancy test result at the screening visit or positive urine pregnancy test at the baseline visit), breastfeeding women, or women planning a pregnancy during the study or 12 weeks after the study drug injection.  14. Subjects who have donated ≥ 500 mL of blood in the 3 months before dosing.  15. Participating or participated in any other study with an investigational drug or device within the past 8 weeks (or 5 half-lives of the investigational drug, whichever is longer) before the screening visit, or is in an exclusion period (if verifiable) from a previous study.  Planned Sample  Size:  From previous studies conducted with nemolizumab, inter-subject standard deviation is expected to be approximately 38.5%, which provides an inter-subject variability coefficient of variation (CV) for the primary PK parameters of 40%. A sample size of 96 subjects per arm (AI or DCS) should provide a 90% power of claiming the bioequivalence between AI and DCS administrations within the range 80.00 to 125.00% for the primary PK parameters with the expected geometric mean ratio of .95.  Approximately 192 healthy subjects are planned to be randomized in this study.  Investigational  Drug:  Nemolizumab (CD14152) 30 mg will be provided for injection for subcutaneous use only after reconstitution in a single-use, prefilled DCS or in a single-use, prefilled AI. Subjects will receive a 60-mg dose of nemolizumab via 2 subcutaneous injections of 30 mg each at the baseline/Day 0 visit  Study Duration:		
11. History of alcohol or substance abuse within 6 months of the screening visit.  12. Planned or expected major surgical procedure during the clinical study.  13. Pregnant women (positive serum pregnancy test result at the screening visit or positive urine pregnancy test at the baseline visit), breastfeeding women, or women planning a pregnancy during the study or 12 weeks after the study drug injection.  14. Subjects who have donated ≥ 500 mL of blood in the 3 months before dosing.  15. Participating or participated in any other study with an investigational drug or device within the past 8 weeks (or 5 half-lives of the investigational drug, whichever is longer) before the screening visit, or is in an exclusion period (if verifiable) from a previous study.  Planned Sample Size:  From previous studies conducted with nemolizumab, inter-subject standard deviation is expected to be approximately 38.5%, which provides an inter-subject variability coefficient of variation (CV) for the primary PK parameters of 40%. A sample size of 96 subjects per arm (AI or DCS) should provide a 90% power of claiming the bioequivalence between AI and DCS administrations within the range 80.00 to 125.00% for the primary PK parameters with the expected geometric mean ratio of 0.95.  Approximately 192 healthy subjects are planned to be randomized in this study.  Nemolizumab (CD14152) 30 mg will be provided for injection for subcutaneous use only after reconstitution in a single-use, prefilled DCS or in a single-use, prefilled AI. Subjects will receive a 60-mg dose of nemolizumab via 2 subcutaneous injections of 30 mg each at the baseline/Day 0 visit  Study Duration:  The expected duration of each subject's participation in the study is up to 16 weeks,		visit or are expected to be vaccinated during the study or during the 12 weeks after the study drug injection, except for non-live seasonal vaccinations (e.g., influenza), COVID-19 and/or emergency vaccinations (e.g., rabies, tetanus), which are permitted
